## **5.0 Analysis Populations**

### **5.1 Definitions of Analysis Populations**

#### **5.1.1 Intention-to-Treat (ITT) Population**

All enrolled subjects who receive at least one dose of study drug will be included in the ITT population. Efficacy analyses and analyses of compliance data will be performed on the ITT population, unless otherwise specified.

#### **5.1.2 Modified Intention-to-Treat (mITT) Populations**

Sensitivity analyses of SVR12 as described in Section 10.5, when applicable, will be performed on the ITT population modified to exclude subjects of multiple genotypes according to the central laboratory or phylogenetic analyses or subjects who received incorrect duration of treatment due to incorrect classification of GT or treatment experience at screening (mITT-GT), and on the mITT-GT population modified to exclude subjects who did not achieve SVR12 for reasons other than virologic failure (i.e., subjects with reasons other than on-treatment HCV virologic failure and relapse) (mITT-GT-VF).

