8.0 Statistical Methods and Determination of Sample Size

8.1 Statistical and Analytical Plans

The primary analysis will occur after all subjects have completed the PT Week 12 Visit or prematurely discontinued the study. The data for the primary analysis will be locked after

data cleaning. Data collected after this lock will be added to a new version of the database which will be cleaned and locked at the end of the study.

SAS[®] (SAS Institute, Inc., Cary, NC) for the UNIX operating system will be used for all analyses. All statistical tests and confidence intervals will be two-sided with an alpha level of 0.05. Descriptive statistics will be provided, such as the number of observations (N), mean, and standard deviation (SD) for continuous variables and counts and percentages for categorical variables.

Data across subjects of all genotypes will be combined for analysis, unless otherwise indicated. Analyses will be performed on the intent-to-treat (ITT) population defined as all enrolled subjects who receive at least one dose of study drug, unless otherwise specified. Sensitivity analyses of the primary efficacy endpoint, when applicable, will be performed on the ITT population modified to exclude subjects of multiple genotypes according to the central laboratory or phylogenetic analyses (mITT-GT), and on the mITT-GT population modified to exclude subjects who did not achieve SVR₁₂ for reasons other than virologic failure (mITT-GT-VF).

No data will be imputed for any efficacy or safety analysis except for analyses of SVR endpoints (HCV RNA data) and PRO questionnaires. HCV RNA values will be selected for the analyses of all SVR endpoints (e.g., SVR₄, SVR₁₂, and SVR₂₄) based on defined visit windows. A backward imputation method will be used to impute missing responses for SVR analyses. Imputation of missing responses on PRO questionnaires is described in Section 8.1.3.

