8.1.2.2 Secondary Efficacy Endpoints

The secondary efficacy endpoints are:

- The percentage of subjects with on-treatment HCV virologic failure (defined as confirmed increase of > 1 log₁₀ IU/mL above nadir during treatment, confirmed HCV RNA ≥ 100 IU/mL after HCV RNA < LLOQ during treatment, or HCV RNA ≥ LLOQ at the end of treatment with at least 6 weeks of treatment), and
- The percentage of subjects with post-treatment relapse (defined as confirmed HCV RNA ≥ LLOQ between end of treatment and 12 weeks after the last dose of study drug among subjects who completed treatment as planned with HCV RNA < LLOQ at the end of treatment, excluding re-infection), and
- The percentage of HCV/HIV co-infected subjects (determined at Screening) achieving SVR₁₂.

For the analysis of relapse, a subject enrolled to receive 12 weeks of treatment is considered to have completed treatment if study drug duration is 77 days or more, and a subject enrolled to receive 16 weeks of treatment is considered to have completed treatment if study drug duration is 105 days or more.

The percentages of subjects with on-treatment virologic failure, post-treatment relapse, and SVR₁₂ will be calculated along with two-sided 95% Wilson score confidence intervals.

In addition, a summary of reason for SVR₁₂ non-response (e.g., on-treatment virologic failure, relapse, re-infection) will be provided for the set of all subjects and for the set of HCV/HIV co-infected subjects.

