### **Definitions for Efficacy Endpoints**

A confirmed quantifiable value during treatment is defined as any two consecutive HCV RNA measurements  $\geq$  LLOQ (or 100 IU/mL for **Breakthrough**), either both during treatment or at the final treatment measurement and the next consecutive post-treatment measurement. A confirmed quantifiable post-treatment value is defined as any two consecutive post-treatment HCV RNA measurements  $\geq$  LLOQ.

**Breakthrough** = confirmed HCV RNA  $\geq$  100 IU/mL after HCV RNA < LLOQ during the Treatment Period; or confirmed increase from nadir in HCV RNA (two consecutive HCV RNA measurements > 1 log10 IU/mL above nadir) at any time point during the Treatment Period. A single breakthrough value ( $\geq$  100 IU/mL or > 1 log10 above nadir) followed by lost to follow-up also will be considered a breakthrough (i.e., will not require confirmation).

**EOT failure** = HCV RNA  $\geq$  LLOQ at end of treatment with at least 6 weeks of treatment, where the HCV RNA value must be collected on or after Study Drug Day 36 and study drug duration  $\geq$  36 days.

**On-treatment HCV virologic failure** = **Breakthrough** or **EOT failure**; if a subject meets both definitions of **Breakthrough** and **EOT failure**, he or she will be categorized as **Breakthrough** only.

**SVR4** = HCV RNA  $<$  LLOQ in the SVR4 window (4 weeks after the last actual dose of study drug) without any confirmed quantifiable ( $\geq$  LLOQ) post-treatment value before or during that SVR window.

**SVR12** = HCV RNA  $<$  LLOQ in the SVR12 window (12 weeks after the last actual dose of study drug) without any confirmed quantifiable ( $\geq$  LLOQ) post-treatment value before or during that SVR window.

**SVR24** = HCV RNA  $<$  LLOQ in the SVR24 window (24 weeks after the last actual dose of study drug) without any confirmed quantifiable ( $\geq$  LLOQ) post-treatment value before or during that SVR window.

**Relapse12** = confirmed HCV RNA  $\geq$  LLOQ between end of treatment and 12 weeks after last actual dose of study drug (up to and including the SVR12 assessment time point) for a subject with HCV RNA  $<$  LLOQ at Final Treatment Visit who completed treatment and has post-treatment HCV RNA data available, excluding reinfection as described below.

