**Relapse24** = confirmed HCV RNA  $\geq$  LLOQ within the SVR24 window for a subject who achieved SVR12 and has HCV RNA data available in the SVR24 window, excluding reinfection.

**Relapseoverall** = confirmed HCV RNA  $\geq$  LLOQ between end of treatment and up to and including the last HCV RNA measurement collected in the PT Period for a subject with HCV RNA  $<$  LLOQ at Final Treatment Visit who completed treatment and has post treatment HCV RNA data available, excluding reinfection.

Only subjects who have at least one post-treatment HCV RNA value will be included in analyses of relapse. For the analyses of relapse, completion of treatment is defined as a study drug duration of 77 days or greater for subjects assigned to 12 weeks of treatment and 105 days or greater for subjects assigned to 16 weeks of treatment. If the last available post-treatment value is  $\geq$  LLOQ, then the subject will be considered a relapse (i.e., will not require confirmation).

HCV reinfection is defined as confirmed HCV RNA  $\geq$  LLOQ after the end of treatment in a subject who had HCV RNA  $<$  LLOQ at Final Treatment Visit, along with the post-treatment detection of a different HCV genotype, subtype, or clade compared with baseline, as determined by phylogenetic analysis of the NS3 or NS5A, and/or NS5B gene sequences. Reinfection in the case of the same HCV subtype is defined as a clade switch, as indicated by the lack of clustering between the baseline and post-treatment sequences by phylogenetic analysis. If phylogenetic analysis is not possible due to technical difficulties, HCV reinfection may be determined with a confirmed HCV genotype or subgenotype switch by the Versant HCV Genotype Inno-LiPA Assay v2.0 or Sanger assay.

Post-treatment relapse is defined as described earlier (**Relapse12**, **Relapse24**, **Relapseoverall**), and no genotype, subtype, or clade switch compared with baseline as determined by phylogenetic analysis of the NS3 or NS5A gene sequences. If phylogenetic analysis is not possible due to technical difficulties, the subject will be defined as having a post-treatment relapse unless an HCV genotype or subgenotype switch is confirmed by the Versant HCV Genotype Inno-LiPA Assay v2.0 or Sanger assay.

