### **Reasons for SVR12 Non-Response**

Subjects who do not achieve SVR12 (SVR12 non-responders) will be categorized as having:

1. On-treatment HCV virologic failure (see **On-treatment HCV virologic failure** definition; if a subject meets both definitions of **Breakthrough** and **EOT failure**, he or she will be categorized as **Breakthrough** only);
2. Relapse12;
3. Prematurely discontinued study drug with no on-treatment HCV virologic failure (defined as any SVR12 non-responder who prematurely discontinued study drug [study drug duration < 77 days for subjects assigned to 12 weeks of treatment, and < 105 days for subjects assigned to 16 weeks of treatment] and did not meet the **On-treatment HCV virologic failure** definition);
4. HCV reinfection (see definition described earlier) ;
5. Missing follow-up data in the SVR12 window (defined as any subject who completed study drug without data in the SVR12 window after applying the imputation rules and not meeting the definitions of [1], [2], [3], or [4]);
6. Other (defined as any SVR12 non-responder not meeting the definitions of [1] – [5]).

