The summaries described above will be performed for the set of all subjects and for the geographic region of China.

A logistic regression model will be used to explore the associations between each of the subgroup variables and SVR12 by fitting a logistic regression model on all subjects in the mITT-GT-VF population. Among all candidate predictors, continuous measurements will be used where possible (e.g., continuous baseline log10 HCV RNA level, continuous age, continuous BMI) in the logistic regression model. A stepwise logistic regression approach will be used to assess the strength of each subgroup variable in predicting SVR12, with a significance level of 0.10 to enter and remain in the model.

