## **10.7 Additional Efficacy Analyses**

The ITT population will be used to summarize the following additional efficacy endpoints for the set of all subjects and for the geographic region of China:

- The percentage of subjects with HCV RNA < LLOQ at each post-baseline visit in the Treatment Period (using data as observed);
- The percentage of subjects with SVR4;
- A summary of reasons for SVR4 non-response (e.g., on-treatment virologic failure, relapse, re-infection, other);
- The percentage of subjects with HCV virologic failure through PT Week 12 (i.e., the SVR12 non-responders due to on-treatment virologic failure or Relapse12);
- The percentage of subjects with SVR24\*;
- A summary of reasons for SVR24 non-response (e.g., on-treatment virologic failure, relapse, re-infection, other)\*;

- The percentage of subjects who relapsed after achieving SVR12 (**Relapse24**).

\* These endpoints will be summarized for the HCV/HIV co-infected subjects (determined at Screening) within the populations/groups identified above.

In the above analyses for SVR, HCV virologic failure, and relapse, the number and percentage of subjects along with a two-sided 95% Wilson score CI will be calculated. Imputations for missing data will be performed as described in Section 6.3 for analysis of SVR, HCV virologic failure, and relapse. All other endpoints will be presented using data as observed.

As additional endpoints, the secondary endpoints will be summarized for the geographic region of China. A summary of the subjects who completed treatment and relapsed (defined as **Relapseoverall**) will be prepared displaying the number of subjects relapsing overall and by SVR visit window (within the SVR4, SVR12, SVR24 windows or after SVR24 window), including the subject number and the SVR visit window corresponding to the first HCV RNA value of those indicating the occurrence of relapse. A similar listing will be prepared for subjects who prematurely discontinued treatment and relapsed after having HCV RNA < LLOQ at their Final Treatment Visit. These summaries will be performed for the overall ITT population and for the geographic region of China within the ITT population.

Listings of subject numbers with reason for non-response will be prepared for the SVR endpoints.

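### A documented post-treatment rebound after early stopping is classed as non-virologic, so it drops out of mITT-GT-VF and the Week 12 virologic-failure count and can be recoded as a success

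*SAP*

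**What the plan says.** SAP 5.1.2 builds mITT-GT-VF by dropping subjects who missed SVR12 "for reasons other than virologic failure (i.e., subjects with reasons other than on-treatment HCV virologic failure and relapse) (mITT-GT-VF"). Protocol 8.1 has the same population in shorter form: "for reasons other than virologic failure (mITT-GT-VF").

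Four other rules in the SAP decide who that affects.

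- **SVR12 (10.1)** is timed from the last actual dose and has no completion requirement.
- **Relapse12 (10.1)** is open only to a subject below LLOQ at the Final Treatment Visit "who completed treatment and has post-treatment HCV RNA data available, excluding reinfection as described below". For this purpose, "completion of treatment is defined as a study drug duration of 77 days or greater for subjects assigned to 12 weeks of treatment", with 105 days for the 16-week group.
- **Reason 3 for SVR12 non-response (10.1)** takes any non-responder "who prematurely discontinued study drug [study drug duration < 77 days for subjects assigned to 12 weeks of treatment" (105 days for 16 weeks) who did not meet the on-treatment failure definition. It sets no condition on post-treatment HCV RNA.
- **Virologic failure through PT Week 12 (10.7)** counts on-treatment failure and Relapse12 only.

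The SAP does foresee the subjects at issue. In 10.7, after the relapse summary for completers, it adds: "A similar listing will be prepared for subjects who prematurely discontinued treatment and relapsed".

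**The concern.** An early stopper who was suppressed at the Final Treatment Visit and then became quantifiable has had a virologic event, and 10.7 itself says such subjects relapsed. Because of treatment duration alone, the event is filed under a non-virologic reason and the subject is removed from mITT-GT-VF. An early stopper with the same exposure who is cured stays in. For early stoppers without on-treatment failure, membership of the population therefore depends on the outcome being estimated.

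The population has several uses. It is a planned sensitivity population for the primary endpoint (SAP 10.5). It is the base for the stepwise predictor analysis, which works by "fitting a logistic regression model on all subjects in the mITT-GT-VF population" (10.6). It is also the base for the Fisher tests of baseline polymorphisms in subjects from South Korea (10.8), where about 40 are planned. Few virologic failures are expected, so one misfiled event is a sizeable share of them.

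The second method in 10.5.1 goes further: it recodes everyone in Reason 3 as an SVR12 success, with no exception for a documented rebound.

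**Working it through.** **1. The plan's own figure.** SAP 4.3 assumes 95% among 160, i.e. 152/160. Normal approximation: 0.95 ± 1.96 × √(0.95 × 0.05 / 160) = 0.95 ± 0.0338, or 91.62% to 98.38%. This reproduces the stated 91.6% to 98.4%.

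**2. Tracing early stoppers through the definitions** (SAP 5.1.2, 10.1, 10.5.1, 10.7):

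| Early stopper | ITT, mITT-GT | mITT-GT-VF | Virologic failure, 10.7 | 10.5.1, second method |
|---|---|---|---|---|
| Reaches SVR12 | responder | kept, responder | no | success |
| Breakthrough, or EOT failure at ≥ 36 days | failure | kept, failure | yes | failure |
| < LLOQ at Final Treatment Visit, then post-treatment rebound, not reinfection | failure | **removed** | **no** | **success** |
| No data in the SVR12 window, no on-treatment failure or documented rebound | failure | removed | no | success |

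Among early stoppers without on-treatment failure, every non-responder is removed, so the SVR12 rate left in mITT-GT-VF is 100% by construction. With 2 cured and 2 rebounding, it shows 2/2 where ITT shows 2/4.

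The later time point is handled differently. Relapse24 carries no completion condition, and the SVR24 premature-discontinuation reason exempts subjects who meet Relapse24. An early stopper who reaches SVR12 and rebounds in the SVR24 window is therefore a relapse, while one who rebounds by the SVR12 assessment is not.

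**3. Size.** The documents give no rate of rebound in early stoppers, so the split below is an assumption. Take 152/160 responders and 8 non-responders: v with on-treatment failure or Relapse12, r early stoppers with post-treatment rebound, and m = 2 with missing follow-up, so v + r = 6. The mITT-GT-VF rate is 152/(152 + v) as written and 152/(152 + v + r) if rebounds are kept. The virologic-failure percentage is v/160 as written and (v + r)/160 if rebounds are counted.

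| r | mITT-GT-VF as written | Rebounds kept | Virologic failure as written | Rebounds counted |
|---|---|---|---|---|
| 0 | 152/158 = 96.2% | 96.2% | 3.75% | 3.75% |
| 1 | 152/157 = 96.8% | 96.2% | 3.13% | 3.75% |
| 2 | 152/156 = 97.4% | 96.2% | 2.50% | 3.75% |
| 3 | 152/155 = 98.1% | 96.2% | 1.88% | 3.75% |
| 4 | 152/154 = 98.7% | 96.2% | 1.25% | 3.75% |

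Each rebound moves the first rate by about 0.6 points and the second by 1/160 = 0.625 points.

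**4. The same at a higher response rate.** The cirrhotic columns of Protocol Tables 6 and 8 hold 281 subjects (165 non-GT3, 116 GT3), with 4 virologic failures and 3 other non-responders. Scaled to 160: 4/281 × 160 = 2.3 and 3/281 × 160 = 1.7. Suppose 156 responders, 2 virologic failures, 1 early stopper with rebound and 1 subject without data. As written the rate is 156/158 = 98.7% with 2 virologic non-responders. With the rebound kept it is 156/159 = 98.1% with 3.

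**5. SAP 10.5.1, second method.** With v = 4, r = 2, m = 2, the as-written rate is (152 + 2 + 2)/160 = 97.5%. If rebounds stay failures it is (152 + 2)/160 = 96.25%.

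**The case against.** The strongest reply is that dropping non-virologic failures is the declared purpose of mITT-GT-VF, and that rebound after truncated exposure says little about the regimen taken as planned. The completer-only relapse rule also comes from the protocol: 8.1.2.2 counts relapse "among subjects who completed treatment as planned with HCV RNA" below LLOQ, and 8.1.4 defines virologic failure as on-treatment failure or post-treatment relapse. This stands as far as it goes. There is no conflict between protocol and SAP, and Relapse12 should not be altered. It does not explain why cured subjects with the same truncated exposure are kept, or why a documented rebound should count as a success in 10.5.1.

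The subjects are also not hidden. They are failures in ITT and mITT-GT, and they appear in the reasons-for-non-response summary and listings (10.4), the list of exclusions (10.5) and the listing in 10.7. Where post-treatment HCV RNA reaches 1000 IU/mL, those from South Korea and GT1 subjects from China are sequenced as non-PVF (10.8). A reader could rebuild the alternative count by hand, but none of this changes the reported rates.

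The expected numbers are small and uncertain. The 281 source subjects are 41% GT3, and 3 of the 4 failures were treatment-experienced GT3. Reweighted to the planned mix: GT1 90 × 1/101 = 0.9; GT2 0; GT3 to 6 between 0 and 24 × 3/51 = 1.4. That gives about 0.9 to 2.3 virologic failures. Early stopping looks rare: an interim report of no discontinuations among 82 cirrhotic subjects, and 2/274 for adverse events (Protocol 3.0), or about 1.2 in 160. All of this stands. One rebound is an assumption, not a forecast.

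**Conclusion.** The point holds for one group: subjects who stop before 77 or 105 days with HCV RNA below LLOQ at the Final Treatment Visit and then have post-treatment HCV RNA at or above LLOQ, confirmed or as the last available value, without reinfection. Each one raises the mITT-GT-VF rate by about 0.6 points, lowers the virologic-failure percentage by about 0.6 points, and becomes a success under the second method in 10.5.1. The size rests on an assumed split of non-responders; if no early stopper rebounds, the effect is zero.

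A reader might infer three stronger things that the documents do not support.

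- That all early stoppers with viral rebound are removed. Breakthrough at any duration, and EOT failure at 36 days or more, count as on-treatment failure and stay in.
- That early stoppers are removed only when viraemic. Those with no data in the window are removed too.
- That the main results are biased. The primary ITT SVR12 result, mITT-GT and the protocol-defined secondary endpoints are unaffected.

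The change is cheap and should be settled before outcomes are known, because early stoppers are followed for HCV RNA for 24 weeks (Protocol 5.1.3) and the data will exist.

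**What to change.** - **SAP 10.1:** split Reason 3 into 3a, premature discontinuation with documented post-treatment rebound (HCV RNA below LLOQ at the Final Treatment Visit, then a confirmed or last available value at or above LLOQ, not reinfection), and 3b, premature discontinuation without it.
- **SAP 5.1.2:** keep 3a in mITT-GT-VF as non-responders and exclude 3b as now.
- **SAP 10.7:** show 3a as its own line beside on-treatment virologic failure and Relapse12.
- **SAP 10.5.1, second method:** recode only 3b and missing follow-up as successes, so that 3a stays a failure.
- **SAP 10.8 and 10.6:** state that 3a subjects stay in the non-PVF listings, labelled as 3a. Report the mITT-GT-VF regression and the South Korea polymorphism tests with 3a subjects identified.
- Leave Relapse12 unchanged.

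The cost is SAP wording and one derived category. The mITT-GT-VF rate may be slightly lower and less directly comparable with other studies in the program; giving the as-written rate alongside preserves the comparison. Because 3b is still excluded while cured early stoppers stay, the population becomes less selected on outcome but not free of it.

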### **5.1.3 Safety Population**

All subjects who receive at least one dose of study drug will be included in the safety population. Analyses of safety; demographics; baseline characteristics; medical history; prior, concomitant, and post-treatment medications; and study drug exposure will be performed on the safety population. The safety population will be the same as the ITT population for this study.

### **5.2 Variables Used for Stratification of Randomization**

This study is not randomized. Eligible subjects will be enrolled into a single arm. Therefore, no variables were used for stratification of randomization.

## **6.0 Analysis Conventions**

### **6.1 Definition of Baseline, Final Treatment, and Final Post-Treatment Assessments**

#### **6.1.1 Baseline**

The baseline value refers to the last non-missing measurement collected before the first dose of study drug is received. The protocol specifies that all Day 1 assessments (other than intensive PK samples) are to be performed prior to administering the first dose of study drug. Therefore, all Day 1 assessments for which time is not collected will be assumed to be pre-dose and the baseline value will be the last non-missing measurement collected on or before the first day of study drug administration.

All Day 1 assessments with time available must be before the time of first dose to be considered baseline, and the last non-missing measurement collected before the date and time of the first dose of study drug will be considered the baseline value. If multiple measurements that are prior to dosing are recorded on the same date and with the same time or if time is not available, then the average of these measurements will be considered the baseline value. The same baseline value will be used for analyses of the Treatment and PT Periods.

Safety assessments that are related to a serious adverse event that occurred on the first dose day are excluded when applying this algorithm.

